7.6. Physical Examinations

Physical examinations, including height and weight, will be performed at the time points detailed in Table 1. Any physical examination finding that is judged by the investigator as clinically significant (except at the screening visit) will be considered an adverse event, recorded on the CRF, and monitored as described in Section 7.1.2.

A full physical examination (performed before spirometry) will include at a minimum the following organ systems: general appearance; head, eyes, ears, nose, and throat (HEENT); chest and lung; heart; abdomen; musculoskeletal; skin; lymph nodes; and neurological.

Investigators should pay special attention to clinical signs related to previous serious illnesses.

7.7. Vital Signs

Vital signs (blood pressure [systolic/diastolic], respiratory rate, body temperature, and pulse) will be measured at the time points detailed in [Table 1](#). All vital signs results outside of the reference ranges will be judged by the investigator as belonging to one of the following categories:

- abnormal and not clinically significant
- abnormal and clinically significant

Before blood pressure and pulse are measured, the patient must rest in a supine or semi-erect/seated position for at least 5 minutes (the same position and arm should be used each time vital signs are measured for a given patient). For any abnormal vital sign value, the measurement should be repeated as soon as possible. Any vital sign value that is judged by the investigator as clinically significant will be recorded both on the source documentation and the CRF as an adverse event and will be monitored as described in [Section 7.1.2](#).

In addition, potentially clinically significant values will be predefined by the sponsor for selected vital sign parameters and will be detailed in the statistical analysis plan.

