7.1. Adverse Events

7.1.1. Definition of an Adverse Event

An adverse event is defined as any untoward medical occurrence in a patient or clinical investigation subject administered a pharmaceutical product and which does not necessarily require a causal relationship with this treatment.

An adverse event can, therefore, be any unfavorable and unintended physical sign, symptom, or laboratory parameter that develops or worsens in severity during the course of this study, or significant worsening of the disease under study, or of any concurrent disease, whether or not considered related to reslizumab. A new condition or the worsening of a pre-existing condition will be considered an adverse event. Stable chronic conditions (such as arthritis) that are present before study entry and do not worsen during this study will not be considered adverse events.

Accordingly, an adverse event can include any of the following:

- intercurrent illnesses
- physical injuries
- events possibly related to concomitant medication
- significant worsening (change in nature, severity, or frequency) of the disease under study or other pre-existing conditions
- drug interactions
- events occurring during diagnostic procedures or during any washout phase of this study
- laboratory or diagnostic test abnormalities that result in the withdrawal of the patient from the study, are associated with clinical signs and symptoms or a serious adverse event, require medical treatment or further diagnostic work-up, or are considered by the investigator to be clinically significant

(Note: Abnormal laboratory or diagnostic test results at the screening visit that preclude a patient from entering the study or receiving study treatment are not considered adverse events.)

- events associated with study procedure (eg, clinically significant adrenal insufficiency)

Asthma exacerbation is an efficacy variable for this study and should be captured on the asthma exacerbation CRF. Accordingly, asthma exacerbations should not be recorded as adverse events unless assessed as more severe than the patient's usual disease course. In this case, the investigator should determine if the adverse event is nonserious or serious based on seriousness criteria, as defined in Section 7.1.5. All asthma exacerbations should be recorded on the asthma exacerbation CRF, regardless of severity or whether it meets adverse event criteria.

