7.1.6.1.2. Creatine Phosphokinase/Muscular Adverse Events Case Report Form

Potentially clinically significant CPK elevations (with or without associated symptoms) or myalgia/muscle symptoms will be recorded as an adverse event and documented using the potentially clinically significant CPK/myalgia CRF. A potentially clinically significant CPK is defined as $\geq 3.1 \times$ ULN (grade 3 based on the FDA “Guidance for Industry Toxicity Grading Scale for Healthy Adult and Adolescent Volunteers Enrolled in Preventative Vaccine Clinical Trials”).

If a potentially clinically significant CPK level ($\geq 3.1 \times$ ULN) occurs, the patient should attend an unscheduled visit for a physical examination as well as additional testing, if indicated per investigator judgement. CPK levels will be retested at a minimum of every 7 to 10 days until the elevation is resolved or if agreed with the medical monitor that no further testing is indicated. For $\geq 10 \times$ ULN elevations in CPK, repeat CPK level, urinalysis (including microscopy), serum electrolytes, blood urea nitrogen (BUN), and creatinine will be performed as soon as possible after receipt of the CPK result. Further testing of CPK levels should be undertaken as frequently as needed to manage patient care per investigator judgment but should be at a minimum of every 7 to 10 days as above. Need for repeat urinalysis, serum electrolytes, BUN, and creatinine testing should be determined by the investigator. In addition, need for treatment (eg, administration of iv fluids and urine alkalinization) should be considered by the investigator.

In cases deemed by the investigator to be treatment-related elevations in CPK $\geq 10 \times$ ULN (eg, potentially rhabdomyolysis), study drug discontinuation should occur at least until CPK normalization or longer based on investigator clinical assessment in collaboration with the sponsor.

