7.4. Clinical Laboratory Tests

All clinical laboratory test results outside of the reference range will be judged by the investigator as belonging to one of the following categories:

- abnormal and not clinically significant
- abnormal and clinically significant

A laboratory test result that is judged by the investigator as clinically significant will be recorded both on the source documentation and on the CRF as an adverse event and will be monitored as described in Section [7.1.2](#). An event may include a laboratory or diagnostic test abnormality (once confirmed by repeated testing) that results in the withdrawal of the patient from the study, the temporary or permanent withdrawal of IMP or medical treatment, or further diagnostic workup. (Note: Abnormal laboratory or diagnostic test results at the screening visit that preclude a patient from entering the study or receiving IMP are not considered adverse events.)

In addition, potentially clinically significant values will be predefined by the sponsor for selected laboratory parameters and will be detailed in the statistical analysis plan.

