7.5. Electrocardiography

A 12-lead ECG will be conducted at screening (visit 0), visit 1, and EOT or early withdrawal visit. ECGs should be obtained before other assessments (eg, blood draw and pulmonary function testing) and study drug administration. Standard ECG parameters will be recorded using the site's equipment, and the ECG will be interpreted locally by the Principal Investigator (or qualified physician) as normal or abnormal. If the ECG is read as abnormal, the Principal Investigator will indicate whether or not the abnormality is clinically significant (yes or no) and write in the detailed interpretation/diagnosis. Clinically significant abnormal ECG findings at baseline and screening should be recorded as part of the medical history. Any ECG finding that is judged by the investigator as a clinically significant change compared with a baseline value will be considered an adverse event, recorded on the source documentation and transcribed onto the CRF, and monitored as described in Section 7.1.2.

In addition, potentially clinically significant values will be predefined by the sponsor for selected ECG parameters and will be detailed in the statistical analysis plan.

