#### 8.5. Clinical Laboratory Tests

Clinical laboratory tests (serum chemistry and hematology) will be performed prior to reslizumab administration at the time points detailed in Table 1 of the protocol. Clinical

laboratory tests will be performed using the central laboratory. Specific laboratory tests to be performed are provided in protocol section 7.4.1.

Summary statistics for laboratory tests will be presented at each scheduled visit. Actual values and changes from baseline to each visit will be summarized using descriptive statistics. Shifts (below, within, and above the normal range) from baseline to each visit will be summarized using patient counts and percentages. Shifts from baseline (Grade 0-4) will be provided for creatine phosphokinase (CPK) at each visit, based on the following grading scale:

- **Grade 0:** <1.25 x ULN
- **Grade 1:** 1.25 to 1.5 x ULN
- **Grade 2:** 1.6 to 3 x ULN
- **Grade 3:** 3.1 to 10 x ULN
- **Grade 4:** >10 x ULN

For CPK values  $\geq 3.1 \times \text{ULN}$  (Grade 3-4), investigators will collect additional information promptly from the patient related to symptoms associated with the elevation and any potential alternate causes. This supplemental data will be reported in the patient listings.

The incidence of potentially clinically significant abnormal values will be summarized for laboratory data using descriptive statistics with the criteria specified in [Table 5](#); criteria have been provided for adults and adolescents separately.

Summaries of potentially clinically significant laboratory values will include all relevant post-baseline values (including scheduled, unscheduled, and early termination visits). A post-baseline laboratory value will be considered potentially clinically significant only if it satisfies the specified criteria and is more extreme (farther from the limit) than the baseline value. Listings for potentially clinically significant laboratory data will be presented. If any patient has a positive pregnancy test, relevant information will be supplied in data listings.

A scatter plot will be provided for the baseline and maximum value for CPK.

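### Protocol 7.4, 7.6 and 7.7 make any clinically significant result an adverse event without asking whether it is new or worse, unlike 7.1.1 and 7.5, so stable entry abnormalities can enter the single-arm primary endpoint

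*Protocol*

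**What the plan says.** Three recording rules in the protocol turn on clinical significance alone.

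- Section 7.7: any vital sign value "judged by the investigator as clinically significant will be recorded both on the source documentation and the CRF as an adverse event". There is no exemption.
- Section 7.4: "A laboratory test result that is judged by the investigator as clinically significant will be recorded" in the source and on the CRF as an adverse event. The only exemption is for screening results that keep the patient out of the study or off study drug.
- Section 7.6: "Any physical examination finding that is judged by the investigator as clinically significant (except at the screening visit) will be considered an adverse event".

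Two other sections tie an adverse event to a change from entry.

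- Section 7.1.1 defines an adverse event as something that develops or worsens during the study, and adds: "Stable chronic conditions (such as arthritis) that are present before study entry and do not worsen during this study will not be considered adverse events".
- Section 7.5 sends clinically significant ECG abnormalities found at screening or baseline to medical history. After that, an ECG finding "judged by the investigator as a clinically significant change compared with a baseline value will be considered an adverse event".

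CPK has its own rule in 7.1.6.1.2: "Potentially clinically significant CPK elevations (with or without associated symptoms) or myalgia/muscle symptoms will be recorded as an adverse event", with the threshold at 3.1 x ULN and no reference to baseline. SAP 8.5 uses the same term, potentially clinically significant, for its laboratory tables, but a post-baseline value qualifies there "only if it satisfies the specified criteria and is more extreme (farther from the limit) than the baseline value".

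The primary analysis (protocol synopsis) is the number and percentage of patients with at least 1 adverse event. SAP 8.3 bases the on-treatment summaries on events with onset in the treatment period. It treats a missing or partial start date as on-treatment unless there is contrary evidence, and puts pre-dose events in the listings.

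**The concern.** Sites receive two rules for the same kind of finding. Take a patient on maintenance oral corticosteroids whose glucose or blood pressure is abnormal, clinically significant and unchanged throughout. Under 7.4 or 7.7 read literally, this is an adverse event. Under 7.1.1 it is not. Had it been an ECG abnormality, 7.5 would have sent it to medical history. Such patients are plausible here: protocol 1.1 names hyperglycemia and elevated blood pressure among the effects of long-term oral corticosteroids, and Study 30027 enrolled patients dependent on them.

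The primary endpoint is a simple incidence in an open-label study with no concurrent control. Over-recording is therefore not cancelled by a comparison arm, and differences in reading among about 140 centers go straight into the reported percentage. SAP precedence over the protocol does not help, because it governs analysis and not what sites enter on the CRF. SAP Table 7 lists no change on this point.

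**Working it through.** The plan states no adverse event rate and no prevalence of entry abnormalities, and the sample size is not derived, so there is no figure of the plan's own to reproduce. The check is a reading of the text, followed by an illustration.

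**1. Where the gap can operate.** Scheduled assessments after the first dose (protocol Table 1):

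| Assessment | Occasions | Baseline comparison in the recording rule |
|---|---|---|
| Vital signs, weeks 4 to 36 | 9 | no |
| Serum chemistry, weeks 4, 8, 24, 36 | 4 | no |
| Hematology, weeks 8, 24, 36 | 3 | no |
| Physical examination, end of treatment | 1 | no |
| ECG, end of treatment | 1 | yes |

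That is 9 + 4 + 3 + 1 = 17 occasions without a comparison, against 1 with. Section 7.6 contributes only one of the 17, because it exempts the screening visit. These counts show opportunity only. They do not multiply the endpoint, which counts each patient once.

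**2. How a stable abnormality reaches the primary percentage.** It must be (a) judged clinically significant, (b) recorded under the literal rule, and (c) given a post-dose onset, or a missing or partial date with nothing to show that it began before dosing. With a pre-dose onset, SAP 8.3 sends it to the listings. Step (c) is realistic for seamless patients. Their entry tests may have been done at the parent study's end-of-treatment visit (Table 1, footnote c), so the first assessment specific to this study can be post-dose. No rule says how to date an abnormality that was already there.

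**3. Illustrative size.** Let p be the share of patients with a genuine on-treatment adverse event, and q the share for whom steps (a) to (c) all occur. Both are assumptions: p from 50% to 90%, q from 1% to 10%. N = 360 is the planned enrollment.

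- Reported share, if the two are independent: 1 - (1 - p)(1 - q). Increase: q(1 - p).
- Upper limit, if affected patients have no other adverse event: min(q, 1 - p).

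| p | q | Increase if independent (points; patients of 360) | Upper limit (points; patients) |
|---|---|---|---|
| 50% | 1% | 0.5; 1.8 | 1; 3.6 |
| 50% | 10% | 5.0; 18.0 | 10; 36 |
| 70% | 5% | 1.5; 5.4 | 5; 18 |
| 70% | 10% | 3.0; 10.8 | 10; 36 |
| 90% | 1% | 0.1; 0.4 | 1; 3.6 |
| 90% | 10% | 1.0; 3.6 | 10; 36 |

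The span is 0.1 to 5.0 points under independence and at most 10 points. The independent increase is proportional to q, so another value of q can be substituted directly. Where sites apply 7.1.1, q = 0 and the increase is 0.

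**4. Single terms.** SAP 8.3 tabulates terms with incidence of at least 2%. Since 0.02 x 360 = 7.2, 8 patients put a term in that table.

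**The case against.** The strongest reply is that 7.1.1 is the governing definition and 7.4 to 7.7 merely apply it. Its own examples include test abnormalities that the investigator considers clinically significant, and they follow from the develops-or-worsens definition. Investigators may also class a result as abnormal but not clinically significant. In addition, SAP 8.3 filters on onset, protocol 7.1.2 requires an onset date for every event, exclusion criterion c removes some patients with uncontrolled conditions, and a patient counts once however often a finding is recorded.

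Much of this stands. It limits the effect and rules out saying that entry abnormalities necessarily inflate the endpoint. It does not remove the conflict: the three sections are mandatory in wording and do not refer back to the develops-or-worsens condition, and the section on ECG shows that the authors knew how to state it. The onset filter works only if the onset is dated correctly, which no instruction secures.

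A reader might infer two stronger points from the CPK text. Neither is supported.

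- That SAP 8.5 contradicts the protocol. SAP 8.5 defines laboratory tables and does not govern adverse event recording. It also asks for supplemental information on every CPK value of at least 3.1 x ULN without a baseline condition, so the absolute trigger looks deliberate. For vital signs the nearer SAP text is 8.7, which likewise defines a table.
- That a patient with, say, CPK of 4.0 x ULN at entry and 3.5 x ULN at week 8 is certain to appear as an on-treatment adverse event. The entry value already meets the trigger in 7.1.6.1.2, so the later one may be the same unresolved event with a pre-dose onset, which SAP 8.3 keeps out.

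**Conclusion.** The conflict between 7.4, 7.6 and 7.7 on one side and 7.1.1 and 7.5 on the other is real and should be removed. Its effect on the primary percentage is conditional: it needs literal recording by the site and an onset that is post-dose, missing or partial. Under the assumptions shown (genuine incidence 50% to 90%, counted entry abnormalities 1% to 10%), the increase lies between about 0.1 and 10 points. The top of that range requires that every affected patient has no other adverse event. None of these inputs comes from the documents, so this range is an illustration and not an estimate.

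For CPK, what remains is one term with two definitions. The muscle-disorder adverse event table (SAP 8.3.1.5) and the SAP 8.5 table can differ for the same patient, and a reader should be told why.

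**What to change.** - In 7.4, 7.6 and 7.7, adopt the logic of 7.5: a result or finding is an adverse event if it is judged clinically significant and is new or worse than the last value before the first open-label dose. Findings already present go to medical history.
- State, in the protocol or the CRF completion guide, that the onset of an abnormality already present before the first dose is the date when it was first observed.
- Keep abnormalities carried over from the parent study in the listings. For seamless patients from the reslizumab arm the entry value is an on-drug value, and filing such a finding only as history could hide one that arose on treatment.
- Leave the CPK recording trigger and follow-up testing in 7.1.6.1.2 unchanged. Making the trigger relative to entry could hide persistent on-drug elevations in those same patients. Instead, add a footnote saying that the CPK adverse event table and the SAP 8.5 table define potentially clinically significant differently.

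The cost is one clause in three sections, one line on onset dates, a listing and a footnote. No new data are needed. The reported adverse event percentage may be slightly lower. Stable laboratory and examination abnormalities remain visible in medical history, in the shift tables of SAP 8.5 and 8.6, and in listings.

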7.8. Assessment of Local Tolerability and Pain

Local tolerability at the injection site (eg, pain, erythema, and swelling) will be evaluated.

The following procedures/assessments will be performed during and after administration of study drug:

- Patients will be observed for 1 hour after study injection.
- Evaluation of injection site for reaction will be performed at approximately 1 hour after dosing using the injection site CRF. Clinically significant injection site reactions should be recorded as an adverse event.

8. OTHER ASSESSMENTS

8.1. Immunogenicity Testing

Immunogenicity of reslizumab sc administration will be assessed by qualified study personnel by evaluating the following:

- ADA measurement at baseline and at weeks 8, 24, and 36 or early withdrawal visit to evaluate the long-term immunogenicity of sc reslizumab
- ADA measurement at EOS visit (19 weeks after final dose) to evaluate immunogenicity after study drug washout

Blood samples (5 mL) for the assessment of ADA response will be taken before dosing at the time points indicated in [Table 1](#). A blood sample will also be collected in the event of withdrawal from the study or upon observation of any severe hypersensitivity reaction (eg, anaphylaxis). An unscheduled sample can also be drawn after a serious adverse event if the investigator or sponsor considers appropriate. Drug levels may be measured in the serum samples collected for ADAs to help inform ADA analysis.

Samples will be collected into labeled serum separator tubes and inverted slowly at least 5 times to thoroughly mix the blood with the clotting activation agent. Labels for samples should include study number, patient number, period, custom identification (ID), and nominal visit. Blood samples will be left standing upright at room temperature (20°C to 25°C) to clot for approximately 30 to 60 minutes. Samples should then be centrifuged at a minimum of 1500g for approximately 10 minutes at 4°C until clot and serum are well separated. Samples may be centrifuged at ambient temperature at 1500g for 10 minutes as long as measures are taken as appropriate to maintain ambient temperature during centrifugation.

Separated serum will be transferred, in approximately equal portions, into 2 labeled cryovial tubes (primary Aliquot A and back-up Aliquot B) and stored in an ultra-low freezer at -65°C or lower until they are shipped to a central or bioanalytical laboratory with temperature monitoring. Sample labels should include patient number, custom ID, study number, nominal visit or week, and indication that it is an ADA sample aliquot (A or B). Storage at -15°C to -20°C should not exceed 60 days if a freezer with a temperature of -65°C or lower is not available. The listed temperatures must be maintained. The actual times and dates of sampling will be recorded on the CRF.

8.1.1. Shipment and Analysis of Samples

Serum samples for immunogenicity assessments for all patients will be shipped from the investigational center to the central laboratory, where they will be stored until shipped to the sponsor or its designee for analysis. Samples will be stored in an upright position at $\leq -65^{\circ}\text{C}$ until assayed. The central laboratory will be notified before the shipment of the samples and will be sent the shipping information when the samples are shipped. Aliquot set A samples will be transported with a temperature data logger and frozen with sufficient dry ice by next-day courier to the central laboratory.

Aliquot set B samples will either be sent to the same laboratory as that for aliquot set A on a later day by next-day courier or be retained at the investigational center until the study is completed (unless shipment to another facility is requested by the sponsor).

Samples from reslizumab-treated patients will be analyzed for ADA using appropriately validated methods. The ADA serum samples may be used to measure serum drug concentration if necessary to help ADA analysis. Timing of the initiation of sample analysis will be determined by the Teva Pharmaceuticals bioanalytical department representative responsible for the bioanalysis. The bioanalytical team will not be blinded for this analysis.

Additional details regarding the collection, handling, and shipment of samples for measurement of ADAs are provided in the investigator laboratory manual and its associated specimen collection summary. Further details can be found in [Appendix P](#).

